### 7.1.5 Combination Expansion (Part 3 Cohorts 1-2)

**Table 7.1.5-1: Selection and Timing of Dose for Part 3 Cohorts 1-2**

Study Treatment	Unit dose strength(s)/Dosage level(s)	Dosage formulation Frequency of Administration	Route of Administration
BMS-986277	RD a	C1 to C2: D1, D3, and D5 (up to 2 cycles of 28 days each)	IV
Nivolumab	480 mg	D15 Q4W up to 26 cycles	IV

a RD from Part 2.

Participants will receive BMS-986277 at the dose recommended from the combination escalation phase of the study.

On BMS-986277 dosing days, participants will receive antipyretic prophylaxis predose and postdose (see [Section 7.7.2](#)). This will generally be acetaminophen/paracetamol and/or ibuprofen at a dose and schedule to manage the participant’s clinical condition, providing that it follows the prescribing information for the product(s). Other medications, including diphenhydramine and indomethacin may be used in line with the study site’s standard practice providing they are not excluded concomitant medications (see [Section 7.7.1](#)). Corticosteroid use may be considered under certain circumstances but should be discussed with the Medical Monitor (or designee) prior to initiation.

Furthermore, at Day 1 of Cycle 2, participants will receive an antipyretic plus an H1-antagonist and, following approval from the Medical Monitor (or designee), hydrocortisone 100 mg IV (or equivalent) one hour prior to BMS 986277 dosing and approximately 3 hours postdose.

BMS-986277 and nivolumab will be administered by IV infusion using a syringe pump (nivolumab may also be administered using an infusion bag).

Infusion duration of BMS-986277 will be based on the dose level chosen for Part 2, and will match the infusion duration for that dose level in Part 1. BMS-986277 will be administered over 5 minutes except for the  $3 \times 10^{12}$  vp dose, which will be administered over 15 minutes.

Nivolumab is infused over 30 minutes. Study treatment preparation and administration are described in [Section 7.1](#).

Participants should receive nivolumab at a dose of 480 mg as an approximate 30 minute infusion on Day 15 of each treatment cycle until progression, unacceptable toxicity, withdrawal of consent, completion of up to 26 cycles of treatment, or the study ends, whichever occurs first. Participants should begin study treatment within 3 calendar days of treatment assignment.

At the end of the infusion the administration line should be flushed with normal saline to ensure that the full viral dose has been administered. This flush should only use a sufficient amount of saline to flush the line and should not exceed 30 mL.

Participants can receive prophylactic IV hydration after the end of each infusion, unless clinically contraindicated. Up to 1 L of normal saline may be administered over 4 hours, adjusted to meet the physiological and clinical requirements of the individual participant (eg, participant BMI, concurrent conditions).

Every effort will be made to administer the planned doses of BMS-986277. If a participant is unable to receive a dose on a scheduled day for reasons other than for toxicity, then every effort must be made to reschedule the dosing as early as possible up to a maximum of 3 days after the previous dose. The infusions of BMS-986277 on Day 3 and Day 5 must be administered within 7 days of Day 1, with a minimum of 24 hours required between each of the three infusions.

### **7.1.6 Monotherapy Expansion with Option for Subsequent Nivolumab Treatment (Part 3 Cohort 3)**

**Table 7.1.6-1: Selection and Timing of Dose for Part 3 Cohort 3**

Study Treatment	Unit dose strength(s)/ Dosage level(s)	Dosage formulation Frequency of Administration	Route of Administration
BMS-986277	RD a	C1 to C2: D1, D3, and D5 (up to 2 cycles of 28 days each)	IV
Optional: Nivolumab	480 mg	D1 Q4W up to 26 cycles starting at C3	IV

a RD from Part 1.

In Part 3 Cohort 3, participants will receive an IV infusion of BMS-986277 at the RD determined in Part 1, starting at time zero administered directly into the venous access point using a syringe pump on Days 1, 3, 5 of each cycle. BMS-986277 will be administered over 5 minutes except for the  $3 \times 10^{12}$  vp dose, which will be administered over 15 minutes. The RD from Part 1 will be determined as indicated in [Section 7.1.3](#). Participants should begin study treatment within 3 calendar days of treatment assignment.

On BMS-986277 dosing days, participants will receive antipyretic prophylaxis predose and postdose (see [Section 7.7.2](#)). This will generally be acetaminophen/paracetamol and/or ibuprofen at a dose and schedule to manage the participant's clinical condition, providing that it follows the prescribing information for the product(s). Other medications, including diphenhydramine and indomethacin may be used in line with the study site's standard practice providing they are not excluded concomitant medications (see [Section 7.7.1](#)). Corticosteroid use may be considered under certain circumstances but should be discussed with the Medical Monitor (or designee) prior to initiation.

Participants will receive a maximum of 2 cycles of BMS-986277 monotherapy. Following 2 cycles of BMS-986277 monotherapy, participants may receive optional nivolumab treatment (480 mg Q4W) for up to 26 cycles if eligibility criteria continue to be met (see [Sections 6.1](#) and [6.2](#)) as indicated in [Table 2-5](#). Participants whose disease progresses prior to receiving Cycle 2 of BMS-986277 may also receive nivolumab treatment if eligibility criteria continue to be met, skipping any remaining monotherapy visits and proceeding directly to Cycle 3, optional nivolumab treatment. For participants whose disease has progressed, a minimum of 14 days will be required between the Day 1 BMS-986277 administration (Cycle 1 or Cycle 2) and the start of nivolumab administration. For participants whose disease is responding (complete or partial) per RECIST v1.1 or PCWG3 at the 8 week scan, treatment must be discussed and agreed upon with the Medical Monitor (or designee) prior to the start of the optional subsequent nivolumab treatment.

BMS-986277 and nivolumab (if participant meets subsequent treatment criteria above) will be administered by IV infusion using a syringe pump (nivolumab may also be administered using an infusion bag).

Infusion duration of BMS-986277 will be based on the dose level chosen for Part 1, and will match the infusion duration for that dose level in Part 1. BMS-986277 will be administered over 5 minutes except for the  $3 \times 10^{12}$  vp dose, which will be administered over 15 minutes.

Nivolumab is infused over 30 minutes. Study treatment preparation and administration are described in [Sections 7.1.1](#) and [7.1.2](#).

Participants should receive nivolumab at a dose of 480 mg as an approximate 30 minute infusion on Day 1 of each treatment cycle starting with Cycle 3 until progression, unacceptable toxicity, withdrawal of consent, completion of up to 26 cycles of treatment, or the study ends, whichever occurs first.

At the end of the infusion the administration line should be flushed with normal saline to ensure that the full viral dose has been administered. This flush should only use a sufficient amount of saline to flush the line and should not exceed 30 mL.

Participants can receive prophylactic IV hydration after the end of each infusion, unless clinically contraindicated. Up to 1 L of normal saline may be administered over 4 hours, adjusted to meet the physiological and clinical requirements of the individual participant (eg, participant BMI, concurrent conditions).

Every effort will be made to administer the planned doses of BMS-986277. If a participant is unable to receive a dose on a scheduled day for reasons other than for toxicity, then every effort must be made to reschedule the dosing as early as possible up to a maximum of 3 days after the previous dose. The infusions of BMS-986277 on Day 3 and Day 5 must be administered within 7 days of Day 1, with a minimum of 24 hours required between each of the three infusions.

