## **8 DISCONTINUATION CRITERIA**

### **8.1 Discontinuation from Study Treatment**

Participants MUST discontinue investigational product (and non-investigational product at the discretion of the investigator) for any of the following reasons:

- Participant's request to stop study treatment. Participants who request to discontinue study treatment will remain in the study and must continue to be followed for protocol specified follow-up procedures. The only exception to this is when a participant specifically withdraws consent for any further contact with him/her or persons previously authorized by participant to provide this information
- Any clinical AE, laboratory abnormality or intercurrent illness which, in the opinion of the investigator, indicates that continued participation in the study is not in the best interest of the participant
- Termination of the study by Bristol-Myers Squibb (BMS)
- Loss of ability to freely provide consent through imprisonment or involuntarily incarceration for treatment of either a psychiatric or physical (eg, infectious disease) illness. (Note: Under specific circumstances, a participant who has been imprisoned may be permitted to continue as a participant. Strict conditions apply and BMS approval is required.)
- Pregnancy

- Documented and confirmed disease progression as defined by RECIST v1.1 or PCWG3 (Appendix 7 and 8, respectively) unless participants meet criteria for treatment beyond progression (Section 8.1.2)
  - Clinical deterioration while receiving active study treatment that, in the opinion of the investigator, indicates that continued participation in the study is not in the best interest of the participant
  - Discretion of the investigator
  - Inability to comply with the protocol requirements
  - Individual participants with confirmed CR will be given the option to discontinue study treatment on a case-by-case basis after specific consultation and agreement between the investigator and BMS Medical Monitor (or designee) in settings where benefit/risk justifies discontinuation of study treatment
  - Any drug-related AE occurring at any time that meets DLT criteria as outlined in Section 7.4.1 will require permanent discontinuation except in cases of non-life-threatening AEs that meet DLT criteria and that have been resolved to Grade 1 or baseline. See Section 8.1.1 for considerations regarding resuming treatment.

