### **8.1.2 Treatment Beyond Disease Progression with Nivolumab in Parts 2 and 3**

Accumulating evidence indicates a minority of participants treated with immunotherapy may derive clinical benefit despite initial evidence of progressive disease (PD).

Participants will be permitted to continue nivolumab treatment beyond initial PD defined by RECIST 1.1 or PCWG3 for prostate cancer, as assessed by the investigator, up to a maximum of 2 years from date of first dose of study treatment as long as they meet the following criteria:

- Investigator-assessed clinical benefit
- Tolerance of study treatment
- Stable performance status
- Treatment beyond progression will not delay an imminent intervention to prevent serious complications of disease progression (eg, CNS metastases)
- Participant provides written informed consent prior to receiving additional nivolumab treatment. All other elements of the main consent including description of reasonably foreseeable risks or discomforts, or other alternative treatment options will still apply.
- For participants in Part 3 Cohort 3, progression must be subsequent to start of nivolumab treatment

The assessment of clinical benefit should be balanced by clinical judgment as to whether the participant is clinically deteriorating and unlikely to receive any benefit from continued treatment with nivolumab. If the investigator feels that the participant continues to achieve clinical benefit by continuing nivolumab treatment, the participant should remain on the trial and continue to receive monitoring according to the Schedule of Activities (see [Section 2](#)). All decisions to continue treatment beyond initial progression must be approved by the BMS Medical Monitor (or designee), and an assessment of the risk/benefit of continuing with study therapy must be documented in the study records (see [Appendix 2](#)).

Participants must be re-consented with an ICF addendum or similar document to continue treatment beyond progression. Treatment beyond progression will require continued tumor assessments and scans should continue to be submitted to the imaging core laboratory.

For the participants who continue nivolumab therapy beyond progression, participants will continue to receive monitoring according to the on-treatment assessments in [Section 2](#) and radiographic assessment, per [Section 9.1.1](#) to determine whether there has been continued disease progression or not.

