Further progression is defined as an additional 10% increase in tumor burden with a minimum 5 mm absolute increase from time of initial PD. This includes an increase in the sum of diameters of all target lesions and/or the diameters of new measurable lesions compared to the time of initial PD. Nivolumab treatment should be discontinued permanently upon documentation of further progression.

New lesions are considered measureable at the time of initial progression if the longest diameter is at least 10 mm (except for pathological lymph nodes which must have a short axis of at least 15 mm). Any new lesion considered non-measurable at the time of initial progression may become measureable and therefore included in the tumor burden if the longest diameter increases to at least 10 mm (except for pathological lymph nodes which must have a short axis of at least 15 mm). In situations where the relative increase in total tumor burden by 10% is solely due to

inclusion of new lesions which become measurable, these new lesions must demonstrate an absolute increase of at least 5 mm.

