### **9.1.3 Secondary Efficacy Assessments**

The secondary efficacy assessments will include the ORR (eg, PR + CR), DCR, mDOR, mPFS and PFSR at 8, 16, and 24 weeks (dependent on indication) based on assessment of tumor response using RECIST v1.1 or PCWG3.

ORR is defined as the proportion of all treated participants whose best overall response (BOR) is either a CR or PR. BOR is defined as the best response designation over the study as a whole, recorded between the dates of first dose until the last tumor assessment prior to subsequent therapy. For participants whose treatment continued beyond RECIST v1.1 or PCWG3 defined disease progression, BOR is defined as the best response recorded between the dates of first dose until the time of the initial disease progression defined by RECIST v1.1 or PCWG3. CR or PR determinations included in the BOR assessment must be confirmed by a second scan performed no less than 4 weeks after the criteria for response are first met. For those participants who have

surgical resection, only pre-surgical tumor assessments will be considered in the determination of BOR.

DCR is defined as the proportion of all treated participants who have achieved CR, PR, and SD. BOR for a participant will be assessed per RECIST v1.1 or PCWG3 by BICR and/or by investigator, where available.

mDOR, computed for all treated participants with a BOR of CR or PR, is defined as the time between the date of first response and the date of disease progression or death, whichever occurs first.

PFS for a participant is defined as the time from the first dosing date to the date of first objectively documented disease progression or death due to any cause, whichever occurs first. mPFS and PFSR will be assessed at 8, 16, and 24 weeks (indication dependent).

The proportion will be calculated by the Kaplan-Meier estimate, which takes into account censored data.

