## 2. RESPONSE CRITERIA

### 2.1 Evaluation of Target Lesions

- **Complete Response (CR):** Disappearance of all target lesions. Any pathological lymph nodes (whether target or non-target) must have reduction in short axis to < 10 mm.
- **Partial Response (PR):** At least a 30% decrease in the sum of diameters of target lesions, taking as reference the baseline sum diameters.
- **Progressive Disease (PD):** At least a 20% increase in the sum of diameters of target lesions, taking as reference the smallest sum on study (this includes the baseline sum if that is the smallest on study). In addition to the relative increase of 20%, the sum must also demonstrate an absolute increase of at least 5 mm. (Note: the appearance of one or more new lesions is also considered progression).
- **Stable Disease (SD):** Neither sufficient shrinkage to qualify for PR nor sufficient increase to qualify for PD, taking as reference the smallest sum diameters while on study.
- **Not Evaluable (NE):** If one or more target lesions cannot be measured or adequately assessed as either fully resolved or too small to measure (due to missing or poor quality images), and the sum of diameters of the remaining measured target lesions (if any) has not increased sufficiently to meet Progressive Disease as defined above.

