# 5.2.1 Preliminary Anti-Tumor Activity

Changes in tumor measurements and tumor response will be measured based on RECIST v1.1 (all indications except PRC) or PCWG3 (PRC participants only), hereafter referred to collectively as "RECIST 1.1/PCWG3". Tumor assessments will be performed at baseline, and then approximately every 8 weeks (all indications except PRC) or every 8 weeks for 24 weeks and then every 12 weeks afterward (for PRC participants). Tumor assessment should continue until disease progression (ideally confirmed with second assessments obtained at least 4 weeks apart) or discontinuation of study treatment, withdrawal from study, or start of subsequent anticancer treatment, whichever occurs later. For PRC participants, any clinical progression due to symptomatic skeletal events detected during bone scans may be counted as a progression event.

The following set of efficacy study-level endpoints will be used:

- **Objective Response Rate (ORR)**: The ORR is defined as the total number of participants whose best overall response (BOR) is either a complete response (CR) or partial response (PR) divided by the total number of participants in the population of interest (eg, all treated participants or response-evaluable participants).
  - The BOR for a participant will be assessed by investigator and/or by BICR, where available.
    - ♦ For interim analyses or internal monitoring of efficacy before the final BOR can be determined, the BOR (including a category for unconfirmed responses still in follow-up) may be derived using an internal algorithm.
  - The BOR for a participant is defined as the best response designation recorded between the date of first study drug administration and the date of first objectively documented progression per RECIST 1.1/PCWG3 or date of subsequent anticancer therapy, whichever occurs first.
    - ♦ For those participants who have surgical resection, only pre-surgical tumor assessments will be considered in the determination of BOR.
    - For participants without documented progression or subsequent anticancer therapy, all available response designations will contribute to the BOR assessment.
    - ♦ For participants who continue treatment beyond progression or begin subsequent anticancer therapy, the BOR should be determined based on response designations recorded up to the time of the initial RECIST 1.1/PCWG3-defined progression or subsequent anticancer therapy, whichever occurs first.

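### Part 3 Cohort 3: Protocol 8.1 does not accommodate the nivolumab crossover after progression that 7.1.6 allows, and, separately, the response rate counts nivolumab responses only without prior documented progression

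*Protocol*

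**What the plan says.** Protocol 5.1.3 and 7.1.6 let Cohort 3 participants who progress on BMS-986277 go on to nivolumab if they remain eligible. Progression in either monotherapy cycle is foreseen: "For participants whose disease has progressed, a minimum of 14 days will be required between the Day 1 BMS-986277 administration (Cycle 1 or Cycle 2"); this gap runs to the first nivolumab dose. Nivolumab then continues "on Day 1 of each treatment cycle starting with Cycle 3 until progression, unacceptable toxicity, withdrawal of consent". No visible text says which scan that progression is measured from, and Table 2-5 keeps imaging on an 8-weekly schedule counted from the first study dose.

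Protocol 8.1 lists documented and confirmed progression as a mandatory reason to stop investigational product, "unless participants meet criteria for treatment beyond progression (Section 8.1.2"). Section 8.1.2 adds a restriction: "For participants in Part 3 Cohort 3, progression must be subsequent to start of nivolumab treatment". Participants treated past progression stop nivolumab at further progression, defined as "an additional 10% increase in tumor burden with a minimum 5 mm absolute increase from time of initial PD".

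Appendix 7, section 2.1, measures progression "taking as reference the smallest sum on study (this includes the baseline sum if that is the smallest on study") and partial response from the baseline sum. Appendix 8 uses the same rule for soft tissue in prostate cancer.

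For treatment past progression, Protocol 9.1.3 says "BOR is defined as the best response recorded between the dates of first dose until the time of the initial disease progression". SAP 5.2.1 closes the window at the "date of first objectively documented progression per RECIST 1.1/PCWG3 or date of subsequent anticancer therapy, whichever occurs first". The secondary ORR is built on this best overall response (BOR).

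**The concern.** The nivolumab step in Cohort 3 is there to explore sequential dosing (Protocol 5.1), and investigators make treatment decisions by RECIST v1.1 or PCWG3 (Protocol 9.1). Two things look unsettled.

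- **Stopping.** Section 7.1.6 permits a crossover after progression that the progression bullet in 8.1 does not accommodate. After crossover, a tumour that nivolumab has merely stabilised can still meet the progression definition because of growth that happened before nivolumab.
- **Reporting.** The Cohort 3 ORR treats a nivolumab response differently according to whether progression had been documented beforehand. It then describes neither BMS-986277 alone nor the sequence.

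At stake are treatment decisions for individual participants and the meaning of a descriptive secondary endpoint.

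**Working it through.** **The plan's own Cohort 3 figure.** Protocol Table 10.1.2.3-1 gives 68% for N = 12 and a log-scale standard deviation of 0.5. With SE = 0.5 × √(2/12) = 0.204, Φ(ln 1.2/SE) − Φ(ln 0.8/SE) = 67.7%. The figure reproduces and does not depend on tumour response, so this point leaves it untouched.

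**Stopping rule, side by side.** Section 7.1.6 allows nivolumab after progression on BMS-986277. Section 8.1 says stop unless 8.1.2 applies. Section 8.1.2 applies in Cohort 3 only to progression after nivolumab has begun. The crossover is therefore allowed in one section and not excepted in the other.

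**Re-reading as progression.** Let N be the smallest sum and (1+g)N the sum at crossover. The progression threshold is max(1.20N, N + 5 mm); the 20% term governs when N is 25 mm or more. To leave progression, the sum must shrink by more than 1 − 1.20/(1+g):

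| Sum at crossover vs smallest | N ≥ 25 mm | N = 20 mm (threshold 25 mm) |
|---|---|---|
| +30% | 7.7% | 3.8% (from 26 mm) |
| +40% | 14.3% | 10.7% (from 28 mm) |
| +60% | 25.0% | 21.9% (from 32 mm) |

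At +25% with N ≥ 25 mm the figure is 4%; at exactly +20% any shrinkage suffices. If the progression included a new lesion, target shrinkage cannot reverse it. Prostate bone disease is less affected, because Appendix 8 compares later bone scans with the first post-treatment scan.

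**Reference and BOR window are separate.** Assume baseline = smallest sum = 100 mm and progression at 125 mm.

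- Unchanged at 125 mm: +25%, progression as written; 0%, stable if measured from the crossover scan.
- Fall to 87.5 mm: −12.5% from baseline, stable as written; −30% from the crossover scan, partial response.
- Fall to 70 mm: response-sized under either reference, yet not counted, because BOR closed at 125 mm.

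The last line shows that a new reference alone would not bring the response into the ORR.

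**Who is counted.** Protocol Section 7 names nivolumab as study treatment, so I do not read it as the subsequent therapy that closes BOR. Participants without documented progression keep an open window and their nivolumab responses count. With r prior radiographic progressors among 12, nivolumab response rate p, no response to BMS-986277 and all 12 starting nivolumab, expected ORR = p(12 − r)/12.

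| p | r = 3 | r = 6 | r = 9 |
|---|---|---|---|
| 20% | 15% | 10% | 5% |
| 40% | 30% | 20% | 10% |

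The rates 20% and 40% are the protocol's mid-CD8 figures, borrowed because none is given for CD8 ≥ 20%; r is assumed. One response in 12 is 8.3 percentage points, and the exact 95% interval for 0/12 already runs from 0 to 26.5%.

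**Timing.** Cycle 2 can start on Day 29, before the first scheduled scan, so progression before Cycle 2 will be clinical or found on an unscheduled scan. Under SAP 5.2.1, clinical deterioration alone is not objective progression, so BOR stays open. With no unscheduled scan, the latest scan is the screening one, up to 28 + 14 = 42 to 28 + 28 = 56 days old when nivolumab starts on Day 15 to 29. Radiographic progression fits best at week 8. That scan may fall on Day 57 ± 7 (50–64) and C3D1 on Day 57 ± 3 (54–60), so on windows alone the scan could follow the first nivolumab dose by up to 64 − 54 = 10 days.

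**The case against.** Closing BOR at first progression is the study-wide rule for treatment past progression, and not crediting later responses is conservative. Cohort 3 is a pharmacodynamic cohort with no ORR hypothesis. Later responses have other outlets: SAP 8.5 plans iRECIST response rates with intervals, iRECIST duration and PFS, spider and waterfall plots that run past progression, and listings showing change and response duration after initial iRECIST progression. Some exploratory objectives and endpoints are not visible and may cover sequential dosing. SAP v1.0 was written before Cohort 3 existed. The 8-week scan is evidently expected before nivolumab, since responders on it need Medical Monitor agreement first.

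Much of this stands and limits the point. It does not remove it. The iRECIST analysis is exploratory, by central review, conditional on data and not for prostate cancer; plots and listings are not a response rate. The expected order of scan and dose is not stated as a requirement for everyone. The stopping rules and the closure of BOR at progression are in the protocol itself.

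Three stronger readings are tempting and not supported. A reader might infer that the missing reference scan is what keeps later responses out of the ORR; the BOR window does that. A reader might infer that a participant stable on nivolumab must come off; 8.1.2 can plausibly be read so that initial PD means the first progression on nivolumab, which allows continuation with clinical benefit, Medical Monitor approval and renewed consent. And a reader might infer that responses after progression would be invisible; the displays above would show some of them.

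**Conclusion.** The point holds as two separate matters. The crossover in 7.1.6 is not excepted in 8.1, and no visible text sets a reference for progression in the nivolumab phase, so an unchanged tumour after radiographic progression reads as progression again and the participant depends on 8.1.2 to continue. Independently, the secondary Cohort 3 ORR mixes participants whose nivolumab responses count with participants whose responses do not.

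The size is modest: treatment decisions and the reading of one descriptive endpoint in about 12 participants. The shrinkage figures follow from the written thresholds at assumed growth. The ORR percentages are illustrations and not forecasts. If nivolumab were instead read as subsequent therapy, no nivolumab response would count for anyone, and the sequence would still have no measure under the visible secondary definitions. Neither the pharmacodynamic aim nor the sample size is affected. The conclusion rests on the visible text. It is worth correcting because the rules conflict and the correction is cheap.

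**What to change.** **Protocol.** Add the 7.1.6 crossover as an exception to the progression bullet in 8.1. In 7.1.6 and 8.1.2, name the last scan before the first nivolumab dose as the reference for the nivolumab phase: the week-8 scan for those starting at C3D1, or a clinically indicated scan at earlier progression. Lesions present on it count as baseline lesions. State that progression, and initial PD in 8.1.2, are measured from this reference during that phase. Require the week-8 scan before C3D1 dosing, which its existing window allows.

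**SAP.** Version 1.0 makes high-CD8 participants ineligible for Part 3 and must be revised for Cohort 3 in any case. In that revision, report BMS-986277 efficacy up to the last pre-nivolumab scan. Separately, give a descriptive nivolumab-phase BOR and PFS against the new reference, split by prior progression: radiographic, clinical only, none.

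**Cost.** Amendment wording and one more small descriptive table; no extra scans or participants. Early clinical progressors without a recent scan would keep a stale reference, which the table should flag.
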